4.5.3 Treatment

AK002 or placebo administered to subjects on Days 1, 29, 57, 85, 113, and 141.

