4.5.5 Strategy for Handling Intercurrent Events

If a prohibited/restricted medication is started during the course of the study, the patient may be withdrawn from study treatment and followed for the 12-week follow-up period. In addition, the follow-up EGD may not be performed. Thus, for the analysis of the study product estimand, tissue eosinophil values and TSS scores will be counted as non-responders for binary variables and set to missing for continuous outcomes from the point when an ICE occurs. An appropriate method for handling missing data through statistical modeling (e.g., multiple imputation [MI]) will be used (as detailed in the SAP). The estimand will provide an answer to the question that is crucial to individual subjects:

If I take this study medication as part of my treatment regimen, without adding any further medications that may impact the underlying disease or exit the study prematurely, what improvements in histology and PRO symptoms might be anticipated after 24 weeks?

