5.1 Study Overview

This is a Phase 3, multicenter, randomized, double-blind, placebo-controlled study to evaluate the efficacy and safety of AK002 in patients with EG and/or EoD who have an inadequate response with, lost response to, or were intolerant to standard therapies.

Patients enrolled in the study will receive 6 infusions of placebo or AK002 administered every 4 weeks and will be followed for 12 weeks after the last dose unless patients elect to enter the optional long-term extension study.

Patients will be consented and then screened for 3–5 weeks (18–45 days) prior to Day 1. Patients who meet all eligibility criteria can be enrolled into the study. Patients who do not meet all eligibility criteria at screening or who qualify at screening but are not enrolled may be assigned a new patient identification number and rescreened once. Patients rescreened within 30 days of signing the initial consent will not need to sign a new informed consent form (ICF) providing no changes have been made to the ICF.

The study is designed as follows:

- An 18 to 45-day screening period with baseline evaluations for study eligibility including active symptoms of disease (gathered by the patient reported outcome [PRO] questionnaire completed during screening) and EGD with biopsy.
- Prior EGD may be used for eligibility as long as the EGD occurred within 30 days of the first screening visit for the AK002-016 study and were performed and centrally assessed as

for the AK002-016 study.

- If patients meet histology and symptom eligibility criteria, they will be randomized and stratified by the highest weekly TSS of disease activity recorded during the screening period (<28 or \geq 28 strata) and whether the patient is EoD-only. The IRT will assign patients 1:1 to receive AK002 or placebo; 6 doses will be received.
- Pre-study medications and dietary restrictions should remain unchanged throughout the screening period and throughout the study. Systemic or swallowed steroids above 10 mg daily prednisone (or the equivalent thereof) will not be allowed except as an approved premedication prior to infusion, to treat an IRR that occurs during infusion, or the use is due to unforeseen circumstances when it is deemed medically necessary to treat an unrelated medical condition.
- Eligible patients will receive the first dose of placebo or AK002 (1 mg/kg) on Day 1, with premedication of 60 mg oral prednisone 12–24 hours prior to the start of the infusion.

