- If the study drug is well tolerated (no stopping rules being met), patients will receive 5 additional doses of placebo or AK002 (3 mg/kg) on Days 29, 57, 85, 113, and 141. With the exception of Day 1, steroid premedication will only be allowed with the written approval of the Medical Monitor.
- Patients will remain at the site for at least 1 hour of observation following the end of the infusion.
- During the Treatment period patients will return to the clinic for study visits as described in the Schedule of Events ([Table 1](#)).
- Daily administration of the PRO questionnaire (including any appropriate additional questions) throughout the study and the follow-up period for all patients.
- An EGD with biopsy will be performed on Day 169 (\pm 3) or 28 (\pm 3) days after last dose of study drug if patient terminates early.
- Follow-up will occur for 84 (\pm 3) days after the last dose of study drug unless patients decide to enter the long-term extension study. Follow-up visits for patients opting not to enter the extension study will occur on Day 176 (\pm 3), Day 197 (\pm 3) and Day 225 (\pm 3).
- Patients who satisfactorily complete AK002-016 have the option to receive AK002 in a separate open-label extension study if all eligibility criteria for the extension study are satisfied. Patients who enroll in the AK002-016X extension study may begin the extension study dosing 1 day after completing the Day 176 visit of this protocol.

- Total study duration is approximately 35–37 weeks. For patients entering the AK002-016X extension study, the total study duration may be as short as 28 weeks.
- Patients may enroll in the AK002-016X extension study any time after the Day 176 visit in the main study has occurred. The Day 197 and Day 225 main study visits will occur if the patient does not enroll in the extension study prior to the scheduled date of these visits. A patient enrolling in the AK002-016X study prior to Day 197 will not complete the Day 197 or Day 225 procedures under this protocol. Open-label dosing and follow-up will occur under the AK002-016X extension study.

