- 30) The ET visits should be conducted 28 (± 3), 35 (± 3), 56 (± 3), and 84 (± 3) days after the last dose of study drug or prior to this, if necessary, to ensure compliance with the visit. If only 1 ET visit is possible, EGD and end-of-study blood work may occur on the same day (28 days after last dose and 35 days after last dose visit procedures). If the end-of-study visit occurs more than 35 days after the last dose of study drug, then perform the visit as soon as possible. The procedures listed under the 28-day and 35-day post-study drug visit will be conducted unless otherwise directed by the Medical Monitor.
- 31) The final hematology assessment for AK002-016 **must** be collected **prior to** the subject taking prednisone premedication for AK002-016X. Therefore, dosing in AK002-016X must take place at least 1 day after completion of the Day 176 visit for AK002-016. Subjects may start AK002-016X dosing 1 day after completion of the Day 176 Visit.
- 32) Blood samples for histamine and tryptase to be collected within 1–2 hours of start of symptoms if there is any suspicion of anaphylaxis.
- 33) For patients who do not start the extension study before Day 197 or Day 225, visit procedures will occur according to the AK002-016 study.

6. Criteria for Evaluation

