14.2 Early Discontinuation of Study Drug

A patient may be discontinued from study treatment at any time if the patient, the Investigator, or the Sponsor feels that it is not in the patient's best interest to continue. The following is a list of possible reasons for study treatment discontinuation:

- Patient withdraws consent.
- An AE that in the opinion of the Investigator results in it being in the best interest of the patient to discontinue study treatment.
- Protocol violation requiring discontinuation of study treatment.
- Participation in any other study during the duration of this study.
- Use of a non-permitted concomitant drug, without prior approval from the Medical Monitor.
- Loss of ability to freely provide consent through imprisonment or involuntary incarceration or treatment of either a psychiatric or physical (e.g., infectious disease) illness.

If a patient is withdrawn from treatment due to an AE, the patient will be followed and treated by the Investigator until the abnormal parameter or symptom has resolved or stabilized.

All patients who discontinue study drug treatment should be encouraged to continue on study and complete assessments and procedures according to the 12-week follow-up period in [Table 1](#), if possible (including follow-up EGD).

Reasonable attempts will be made by the Investigator to provide reasons for patient withdrawals. The reason for the patient's withdrawal from the study or all attempts to acquire such, will be specified in the source documents.

15. Statistical Methods and General Considerations

This section outlines the statistical methods to be used for the analysis of the data from the study. A separate Statistical Analysis Plan (SAP), which must be documented as completed prior to unblinding the study, will describe data handling and statistical techniques in full detail and will supersede the statistical methods detailed in the protocol. The SAP will detail any modifications to the analysis plan described below.

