Study Day	Study Day 1 is defined as the date on which a subject took the first dose of study drug. Other study days are defined relative to Study Day 1. For visits prior to the first dose of study drug, Study Day is calculated as Visit Date – Day 1 Date. For visits after the first dose, Study Day is calculated as Visit Date – Day 1 Date +1.
Study Drug	AK002 or placebo administered by IV infusion.
Study Week	Study Week for PRO analysis is defined as 7 days a week starting from the day of first dose (Day 1).
Tissue Eosinophil Responder in Disease Status (2 levels; EG ± EoD, EoD)	For EG with/without EoD subjects: Mean eosinophil count \leq 4 cells/hpf in 5 highest gastric hpf and/or mean eosinophil count \leq 15 cells/hpf in 3 highest duodenal hpf. For EoD subjects: Mean eosinophil count \leq 15 cells/hpf in 3 highest duodenal hpf.
Treatment-emergent	Adverse events reported in the clinical database with a date of onset on or after the start date of the first dose of the study drug.
Treatment Responder	Subject with >30% improvement in TSS from baseline and mean eosinophil count \leq 4 cells/hpf in 5 highest gastric hpf and/or mean eosinophil count \leq 15 cells/hpf in 3 highest duodenal hpf.

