5.4.2 Missing Daily PRO Scores at Weeks 23–24

PRO daily scores will be set to missing if they are collected after subjects have experienced ICE. For the endpoints of change in the weekly average of PRO TSS, when ≥ 4 of 7 daily scores are available, the weekly average score will be calculated using the available daily scores. (See [Appendix 1](#) for justification of allowing weekly average being calculated from ≥ 4 daily scores.) This calculation implies the missing daily scores are the same as the mean of the non-missing daily scores. When ≥ 4 daily scores are missing, the weekly score will be set to missing. For the calculation of the average PRO TSS over Weeks 23-24, if ≥ 1 weekly score is missing, the biweekly average of Weeks 23–24 will be considered missing.

Missing average of Weeks 23–24 TSS will be imputed using the Markov Chain Monte Carlo (MCMC) method. Baseline tissue eosinophil count and PRO TSS, and disease stratum (EG \pm EoD vs. EoD without EG) will be included along with the average biweekly PRO TSS (W01_02, W03_04, W05_06, ..., W21_22, W23_24) in the multivariate distribution construction. The imputation will be carried out for each treatment group separately and will be executed multiple (50) times (MI). The purpose of MI is to account for the imputation variability in the parameter estimates. An example of the SAS code for this imputation follows.

```
proc mi data=TSS seed=1357986420 n impute=50
  out=TSS_IMMPUTED ;
  by TRTMT ;
  class DISEASE_STRAT ;
  mcmc chain=multiple impute=full initial=em nbiter=200 niter=100 ;
  var B_EOS DISEASE_STRAT (3 levels) B_TSS TSS_W01_02 TSS_W03_04
  ... TSS_W21_22 TSS_W23_24 ;
  run ;
```

After the imputation, the least squares mean (LSM) and standard error (SE) are derived from the conventional ANCOVA from each imputed data set.

These LSM and SE are synthesized to derive the imputation variability-adjusted LSM and SE for each treatment group and for the between treatment difference. These synthesized LSM and SE are then used in the hypothesis test for the between treatment difference. An example of the SAS code for the synthesized LSM comparisons between treatment is as follows.

```
ods output ParameterEstimates=LSMDIF ;
proc mianalyze data=DIFF alpha=0.05 ;
  modeleffects LSM ;
  stderr SE ;
run ;
```

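### Follow-up after early stopping is counted from the last dose, so patients who stop after infusions 1–3 have no scheduled diary in Weeks 23–24, the TSS co-primary window

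*Protocol*

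**What the plan says.** **Follow-up.** Protocol 5.1 says patients "will be followed for 12 weeks after the last dose unless patients elect to enter the optional long-term extension study". Table 1, note 30, places the early-termination visits at 28, 35, 56 and 84 (±3) "days after the last dose of study drug or prior to this, if necessary, to ensure compliance with the visit". Protocol 14.2 encourages patients who stop study drug to "continue on study and complete assessments and procedures according to the 12-week follow-up period", if possible. After a prohibited or restricted medication, Protocol 4.5.5 says "the patient may be withdrawn from study treatment and followed for the 12-week follow-up period". The daily questionnaire runs through the study and follow-up (Protocol 5.1). No section keeps it open to Week 24 for a patient who stopped early.

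**Endpoint.** SAP 4.1 states: "Study Week for PRO analysis is defined as 7 days a week starting from the day of first dose". SAP 5.4.2 needs at least 4 of 7 daily scores for a weekly score, and treats the Weeks 23–24 average as missing if either week is missing.

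**Missing data.** SAP 5.4.2 sets scores collected after an intercurrent event to missing and imputes the missing average by MCMC: "The imputation will be carried out for each treatment group separately". SAP 6.11.5 adds a placebo-based analysis and a tipping-point analysis.

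**Intercurrent events.** SAP 4.2.4 lists premature discontinuation from the study and use of prohibited or restricted medication. SAP Appendix 2, part C, lists stopping study drug, but only for an infusion-related reaction, subject withdrawal or the criteria of Protocol 13.10. Protocol 14.2 allows stopping for other reasons, such as an adverse event judged by the investigator to warrant it.

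**The concern.** The endpoint is timed from the first dose, but follow-up of an early stopper is timed from the last dose. The earlier the stop, the further the last planned diary falls before the endpoint window. Patients who complete treatment and do not enter the extension, by contrast, keep the diary to Day 225, which is 57 days past Day 168. The questionnaire is web-based (Protocol Appendix 7) and needs no visit, so there is no evident reason to close it for a patient who is willing to go on.

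Two things are at stake. Some patients may lose an otherwise usable co-primary value because of the schedule alone. And the imputations for early stoppers cannot be compared with anything those patients report in Weeks 23–24. Protocol 2.3 and 3 say infusion reactions are fewer after the first infusion, so stops at the early infusions are plausible, although no stop rate is given. Diaries that were never collected cannot be recovered later.

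**Working it through.** **1. The plan's own figure.** Protocol 15.1: 80 per group, mean reductions of 16.1 and 8.7 points (difference 7.4), SD 12.5; SAP 5.8: two-sided 0.05. Standard error = 12.5 × √(2/80) = 1.976; 7.4/1.976 = 3.744; power = Φ(3.744 − 1.960) = 0.963 (0.961 by noncentral t). The stated 96% is reproduced and is not in dispute.

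**2. The endpoint window.** Week 23 begins on Day 22 × 7 + 1 = 155. Week 24 ends on Day 24 × 7 = 168.

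**3. End of planned diaries.** Protocol 4.5.3 gives the infusion days: "AK002 or placebo administered to subjects on Days 1, 29, 57, 85, 113, and 141". End of follow-up = day of last dose + 84. The ranges use ±3 days on the dose (none on Day 1) and ±3 days on the last visit.

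| Last infusion | Dose day | End of follow-up (range) | Days short of Day 155 | Planned diary days in Weeks 23–24 |
|---|---|---|---|---|
| 1 | 1 | 85 (82–88) | 70 | 0 of 14 |
| 2 | 29 | 113 (107–119) | 42 | 0 of 14 |
| 3 | 57 | 141 (135–147) | 14 | 0 of 14 |
| 4 | 85 | 169 (163–175) | covered | 14 of 14 |
| 5 | 113 | 197 (191–203) | covered | 14 of 14 |
| 6 | 141 | 225 (219–231) | covered | 14 of 14 |

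For infusions 1–3 no use of the visit windows reaches Day 155; the closest is Day 147, 8 days short. For infusion 4 the earliest end, Day 163, leaves only 2 diary days in Week 24, below the 4 required, so the average would be missing.

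**4. What this means by type of stop.**

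- *Stop listed in SAP Appendix 2.* Later scores are set to missing whether or not they were collected. Longer collection would not change the primary estimate. It would supply observed values for checking.
- *Stop not clearly listed*, for example an adverse event other than an infusion reaction. The scores would be usable, but none is scheduled in the window. The patient leaves at about Day 85, 113 or 141 and, under the completion definitions (Protocol 14.1, SAP Table 2), may be recorded as having discontinued the study prematurely. That is an intercurrent event under SAP 4.2.4, here produced by the schedule. If it is not so recorded, SAP 6.11.5, read literally, does not re-impute the value, because it resets only scores tied to an intercurrent event.

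**5. Illustration of size.** Assume a share f of AK002 patients stop and change like placebo (8.7 points), while the others change by 16.1. The difference in all dosed patients is 7.4 × (1 − f):

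- f = 5%: 7.03
- f = 10%: 6.66
- f = 15%: 6.29

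The values of f are assumptions.

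**The case against.** The strongest objection is that the plan does not aim to measure these patients off drug. Protocol 4.5.5 and SAP 4.2.5 ask what happens to a patient who takes the drug without added medication and without leaving early, and post-event scores are discarded to match. For listed events this stands: diaries to Day 168 would leave the co-primary estimate unchanged.

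Other points also stand in part:

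- The tipping-point analysis varies the shift independently by arm, which addresses reliance on missing at random. But its largest shift is to be guided by differences between patients who drop out and those who continue, and no Weeks 23–24 data from stops at infusions 1–3 can inform that.
- The plan does give up to 84 days of diaries after the last dose, so drift toward placebo can be examined at earlier weeks. The first 28 of those days are the normal dosing interval, leaving 56 beyond it, and none falls in the endpoint window.
- The imputation conditions on baseline eosinophils, baseline TSS, disease stratum and earlier biweekly TSS. It does not simply assign the AK002 mean to every stopper.
- Clustering of stops at infusions 1–3 is not shown. Protocol 2.3 describes most reactions as mild to moderate, and premedication is required before infusion 1. Reaction frequency is not stop frequency.
- Power is not threatened: even at f = 15% with all benefit lost and the same SD, it is 88.9%.

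It can also be argued that leaving on Day 85 is itself a premature exit and so already an intercurrent event. That depends on which list is applied, and it would mean that the schedule creates the event.

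**Conclusion.** The calendar gap is certain on the documents' own dates: stops after infusions 1–3 have no scheduled diary in Weeks 23–24, and infusion 4 is at risk only at the earliest visit windows. For stops outside SAP Appendix 2, the schedule itself makes the TSS co-primary missing. For listed stops, what is lost is endpoint-window data to check the within-arm and placebo-based imputations, to inform the tipping-point shifts, or to support an analysis regardless of intercurrent events.

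Three stronger readings are tempting, and the documents do not support them:

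- *That the primary analysis overstates the effect by 0.4 to 1.1 points* (7.4 − 7.03 to 7.4 − 6.29). That gap separates two estimands. It is not an error in the stated one, and it rests on assumed stop rates and full reversion to placebo.
- *That these scores can never be observed.* They are not scheduled to be; nothing forbids collecting them.
- *That no as-randomised estimate is possible.* Stops after infusions 4–6 nominally have observed windows, and placebo-based imputation gives an estimate under its assumption. What cannot be done is to base such an estimate on observed Weeks 23–24 scores for stops at infusions 1–3.

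The size cannot be fixed, because the documents give no stop rate and do not say how many stops would fall outside Appendix 2. This is a worthwhile, low-cost improvement, not a flaw that invalidates the co-primary.

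**What to change.** - **Protocol 14.2 and Table 1:** patients who stop study drug early and remain willing keep completing the daily questionnaire through Day 168, whatever the date of the last dose. No visit or endoscopy is added. Scores from stops that are not intercurrent events then enter the primary analysis as observed.
- **SAP 6.11.6:** add one supplementary ANCOVA of Weeks 23–24 TSS in the MITT population using all observed diaries regardless of intercurrent events. Tabulate observed scores in early stoppers beside the placebo-based imputed values.
- **SAP 4.2.4 and Appendix 2:** reconcile the lists before unblinding, so that each reason for stopping has one status, and state whether leaving at the end of the follow-up counted from the last dose is a premature discontinuation.

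The primary estimand and analysis are otherwise unchanged.

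**Cost.** Up to 168 − 85 = 83, 168 − 113 = 55 or 168 − 141 = 27 extra diary days after infusions 1, 2 and 3, for what may be few patients. A protocol amendment with IRB approval and investigator signatures is needed (Protocol 17.1), with a SAP revision and possibly extended diary compensation (Protocol 17.6). Patients who withdraw consent would still contribute nothing.

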15.1 Sample Size

A total of approximately 160 patients will be enrolled.

First Co-Primary Endpoint: A sample size of 80 patients per treatment group will have >99% power to demonstrate a greater proportion of responders in AK002 patients than in placebo patients, assuming the proportions of responders are 0.6 and 0.1 in AK002 and placebo groups, respectively.

Second Co-Primary Endpoint: A sample size of 80 patients per group will provide 96% power to detect a statistically significant difference between AK002 and placebo in the mean reduction from baseline in TSS score, assuming a mean reduction of 16.1 points on AK002 versus 8.7 points on placebo and a common standard deviation of 12.5 points (AK002-003 data on file). Eighty patients per group will provide 96% power to pick up a difference between placebo and AK002 of 7.4 in TSS with a mean Baseline TSS of 30 and a standard deviation (change from baseline) of 12.5. These assumptions are based on data observed in the Phase 2 AK002-003 study.

15.2 Analysis Populations

The safety population is defined as all patients who are randomized and have received at least 1 infusion of the study drug.

The primary efficacy analysis population is **modified intent-to-treat (MITT) population**, defined as all randomized patients who have received at least 1 infusion of the study drug.

The secondary efficacy analysis population is **per protocol (PP) population**, defined as MITT patients who have received at least 1 infusion of study drug and did not have significant protocol violations possibly interfering with assessment of efficacy. The MITT population will be used for all efficacy analysis. The PP population will be used for the primary endpoints and select secondary endpoints analyses. The Safety population will be used for all safety analysis.

The study statistician along with the study team will review protocol deviations to identify patients to be excluded from the Per Protocol Analysis population.

